General overview: The proposed research will test in a nested case-control study associations of individual metabolites and broader metabolomics profiles as well as counter-regulatory hormones and biomarkers with stress-hyperglycemia (Aim 1). For this analysis patients will be stratified according to the outcome of stress-hyperglycemia (cases) and compared to controls (no hyperglycemia). For Aim 2 a randomized clinical trial will be conducted to examine the effects of exposure to dulaglutide on the prevention of stress-hyperglycemia and the metabolic inflammatory response in the perioperative period, (Fig. 6).

[figure not shown]

Figure 6. General overview. Aim 1 will be tested with a case-control study design. In Aim 2 we will conduct a clinical trial.

Specific Aims

D1. Case – control study

Aim 1. To examine baseline and postoperative metabolic profiles of non-diabetic CABG patients with stress hyperglycemia.

Rationale: the underlying mechanisms leading to stress-hyperglycemia and its association with poor outcomes in cardiac surgery patients are not well understood. We aim to study metabolic signatures associated with hyperglycemia and path-specific biomarkers. We will test the temporal relationships between candidate metabolites/pathways (Table 1) and specific biomarkers with stress-hyperglycemia.

Study design: In a nested case-control study (N=50) we will compare the characteristics of patients developing postoperative stress-hyperglycemia (cases) compared to patients that do not develop stress-hyperglycemia (age-matched controls). A proportion of patients will be derived from the placebo arm of the randomized trial. This design will allow efficient recruitment from our cohort of CABG patients to allow substantial savings in cost

and time. **Case definition:** stress-hyperglycemia is defined as a BG >140mg/dl on arrival to the ICU. Please see additional details in Human Subjects section.

Study Population: we will include patients with ages between 18-80 years without a history of diabetes [BG \leq 125 mg/dl and HbA1c <6.5%] undergoing CABG surgery. Patients will be recruited from three academic hospitals, including Emory University Hospital, Emory Hospital Midtown (EUHM), and Grady M Hospital in Atlanta, GA. [name] (Chief of Division and Director of the CTS Center for Clinical Research) is a key collaborator and will facilitate recruitment and perform CABG surgeries.

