Aim 1.1 Targeted Approach: We will determine cross-sectional and longitudinal changes of ceramides, acylcarnitines, BCAA, and a biomarker panel for CVD outcomes and their relationship with stress hyperglycemia (BG >140mg/dl on ICU arrival). Path-specific biomarkers include: TNF- α and C-reactive protein (inflammation), fibrin degradation products (pro-thrombosis), heat shock protein-70 (cell stress), and suPAR (immune modulation and inflammation). Counterregulatory hormones include: cortisol, glucagon. Glucose, insulin and indexes of insulin sensitivity/insulin resistance: will be derived from glucose, insulin and c-peptide values. **Methods:** Plasma samples will be stored at -80°C until analysis. Serum CRP and FDP including fragments D and E, D -dimer, and additional intermediate cleavage products will be determined (FirstMark, San Diego, CA). Serum HSP-70 will be measured with a sandwich enzyme-linked immunosorbent assay (R&D Systems, Minneapolis, MN). Plasma suPAR levels will be measured using commercially available kits (suPARnostic kit; Virogates, Copenhagen, Denmark). Minimum detectable CRP, FDP, HSP-70, and suPAR have been reported at 0.1 mg/L, 0.06 $\mu\text{g}/\text{mL}$, 0.313 ng/ml, and 0.1 ng/ml, as described previously.⁶⁵⁻⁶⁸ Liquid chromatography tandem mass spectrometry techniques will be used to quantitatively profile ceramides, acylcarnitines, branched chain amino acids (leucine, isoleucine, valine), and aromatic amino acids (tyrosine and phenylalanine) in plasma samples along with standard reference samples. Glucose levels will be analyzed by the hexokinase method (Beckman-Coulter, Los Angeles, CA). Counterregulatory hormones, insulin, C-peptide levels by two-site sequential chemiluminescent immunometric assays. Surrogates of beta cell function (HOMA-B) and insulin resistance (HOMA-IR) will be derived from fasting glucose, c-peptide and insulin.

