Analysis: Student's t test and χ^2 tests will be used when appropriate. Mann-Whitney U or Kruskal-Wallis nonparametric tests will be used for non-normally distributed variables. Analysis will account for age-matching. The relationship between biomarkers and stress-hyperglycemia and surrogates of insulin sensitivity and beta cell function will be determined using the Cox proportional hazards regression in unadjusted models and in models adjusted by gender, and smoking status to evaluate the impact of each 1 U increase in a biomarker risk score based on previously defined cut points for CRP, FDP, HSP-70, and suPAR (3 mg/L, 1.0 $\mu\text{g}/\text{mL}$, 0.313 ng/ml, and 3.5 ng/ml, respectively) as previously described.^{65,66,68}

1.2 Untargeted Analysis: Utilizing untargeted LCMS-derived high-resolution metabolomics (HRM) analysis we aim to identify additional candidate metabolites and new metabolic pathways associated with incident stress hyperglycemia during cardiac surgery. **Methods:** HRM analysis is a major component of my career development plan. Data analysis will be conducted under the supervision of [name]. Data Interpretation will be conducted under the guidance of [name] (expert in metabolism). I will also have local support from [name] for interpretation of metabolomics results, as well as statistical support from [name]. [name] will provide guidance for hands-on use of metabolomics tools. Co-mentors and collaborators are experts in the data management requirements of the LCMS-derived high-resolution metabolomics (HRM) analysis proposed in this project. Serial samples will be collected: at baseline (up to seven days before surgery), at 15 minutes (after cardiac bypass has started for on pump surgeries) or 2hrs after sternum incision (for off pump surgeries), 24hrs, 72-96hrs and 30 days after surgery. Plasma samples will be stored at -80°C until analysis. The methods use UPLC with ultra-high resolution mass spectrometry with a dual chromatography, dual ionization approach with each sample being analyzed with three technical replicates.¹²²⁻¹²⁴

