With advanced data extraction provided by xMSanalyzer and apLCMS, I will be able to also measure a spectrum of high and low abundance metabolites. We will utilize a well-established computational metabolomics workflow with rigorous standard operating procedures outlined in Fig. 7.¹²⁴ Data Selection and Annotation (Biostatistics and Bioinformatics Tools): HRM data will be processed using apLCMS with xMSanalyzer^{125,126}. Feature annotation will be performed using xMSannotator.¹²⁷ xMSannotator provides confidence scores for more than 2,000 metabolites, with more than 300 metabolites having confirmed identities and including most major pathways. The quality of data will be judged based on established rigorous criteria (e.g. coefficient of variation within replicates and QC samples, the percentage of missing values, the percentage of data exceeding detection limits of the machinery, batch-effects, and the percentage of outliers, etc.). Principal Component Analysis (PCA) will be used for batch-effect evaluation and ComBat¹²² will be used for batch- effect correction if necessary. Identifying expressed metabolites across different time points: we will use univariate and multivariate statistical methods, such as linear mixed effects models with post-hoc Tukey tests, LIMMA, and multilevel sparse Partial Least Squares Discriminant Analysis (msPLSDA).^{128,129} Multiple hypotheses testing correction will be performed using the Benjamini-Hochberg method.¹³⁰ Identifying putative biomarkers: we will use a consensus feature selection approach such that metabolic signatures identified by both univariate and multivariate approaches will be used for downstream analyses. K-fold and leave-one-out cross-validation using Support Vector Machine (SVM) will be performed to evaluate predictive accuracy of putative biomarkers. Two-way hierarchical clustering analysis will be performed to identify clusters of correlated metabolic features and to evaluate the ability of the discriminatory features to separate samples based on stress-hyperglycemia. Pathway enrichment analysis: Pathway analysis will be performed with pathway enrichment software for untargeted metabolomics data (Mummichog and MetabNet)^{131,132}. Where appropriate, additional chemical verification will be performed for significant metabolites of interest according to retention time and characteristic ion dissociation (MS/MS) patterns relative to authentic standards. Metabolome-wide association study (MWAS) of specific metabolites will be conducted (MetabNet) to facilitate detection of their related metabolic pathways and network structures in association with glucose levels (continuous) and stress-hyperglycemia as a discrete dichotomous variable.

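### Aim 1.1 names Cox regression for an outcome read once at ICU arrival in a case-control sample of 50; with no event time, the hazard ratio is undefined

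*Combined protocol and SAP*

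**What the plan says.** Section D1, Aim 1.1, Analysis, lists two-group tests and then a regression. Its subject is "The relationship between biomarkers and stress-hyperglycemia and surrogates of insulin sensitivity and beta cell function", and these relationships "will be determined using the Cox proportional hazards regression in unadjusted models and in models adjusted by gender, and smoking status". The effect is to be reported per one-unit increase in a score built from cut points for CRP, FDP, HSP-70 and suPAR. The sentence closes by citing earlier publications.

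The outcome is fixed in D1, Case definition: "stress-hyperglycemia is defined as a BG >140mg/dl on arrival to the ICU". Section E.1.1, Group Assignment / Case Definition, has subjects sorted into cases and controls at that same moment. It calls for 25 age-matched controls; 25 cases is inferred from the total of 50. Further controls are chosen within 3 years of age by reference to the case population as a whole, and no pairs are described. On matching, the Aim 1.1 paragraph says only: "Analysis will account for age-matching". The adjusters it lists are gender and smoking.

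Elsewhere the outcome is treated as binary: Aim 1.2 refers to "stress-hyperglycemia as a discrete dichotomous variable". For the other outcomes in the Cox sentence, Aim 1.1 Methods states: "Surrogates of beta cell function (HOMA-B) and insulin resistance (HOMA-IR) will be derived from fasting glucose, c-peptide and insulin".

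**The concern.** A Cox model compares, at each event time, the subject who has the event with those still at risk. It needs a time for every subject and a set of people at risk at that time. Aim 1 provides neither, because everyone is classified once, at the same clinical moment. HOMA-IR and HOMA-B have no event at all.

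An analyst following the text would have to make up a time variable, and the reported hazard ratio would then depend on that choice and on the software's default for ties. Readers would take the figure as a rate ratio or an odds ratio when it is neither.

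The sentence also leaves open which blood sample supplies the score. In the schedule given under Aim 1.2, only the baseline and intra-operative samples precede ICU arrival; those at 24 h, 72–96 h and 30 days follow it. A score from a later sample cannot be said to predict an outcome already fixed.

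**Working it through.** **The plan's own figure.** No event count, hazard ratio or power is given for the Cox model. The only Aim 1 figure, in E.1.9, is that N=50 suffices for a Wilcoxon test at effect size above 1, alpha 0.05 and power 0.80. Taking two sides and effect size 1, the normal approximation gives 2 × (1.96 + 0.84)² ≈ 15.7, so 16 per group. Dividing by the Wilcoxon efficiency 3/π = 0.955 gives 17. With 25 per group, power is Φ(√(25 × 0.955 / 2) − 1.96) = Φ(1.495) ≈ 0.93 (0.92 by simulation). The statement holds, but it covers a two-group comparison and not the Cox analysis.

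**What a Cox model needs, against what the plan gives.**

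| Needed | In the plan |
|---|---|
| Time origin and event time | None; status is read once, at ICU arrival |
| Censoring rule | None |
| Controls drawn from those at risk at the event time | Controls chosen on age |
| Strata or matched sets | None named; no pairs described |
| Tie method | None |
| An event for HOMA-IR and HOMA-B | Not possible; both are continuous |

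**What a common dummy time does.** Take one binary marker, positive in *a* of 25 cases and *b* of 25 controls.

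- Odds ratio: a(25 − b) / [b(25 − a)].
- Cox with Breslow ties and all times equal: solving the score equation gives [a/(a + b)] / [(25 − a)/(50 − a − b)]. This is the ratio of case fractions in the sample, and it depends on the case:control split set by design.
- Odds ratio divided by the Cox figure: [1 + a/b] / [1 + (25 − a)/(25 − b)]. This exceeds 1 whenever a > b, so the Cox figure is pulled toward 1.

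**Size, by simulation.** Assumed inputs, none from the documents: score 0–4, true odds ratio 2.0 per unit, 25 v 25, ten control-score distributions (binomial with several success probabilities, uniform, unequal marker prevalences, correlated markers), unadjusted models, age not modelled, 2,000 samples per setting. Medians, with the range over the ten distributions:

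| Model | Estimate per unit |
|---|---|
| Logistic | 2.03–2.07 |
| Cox, common time, discrete ties | 2.00–2.04 |
| Cox, common time, stratified by (random) pair | 2.02–2.09 |
| Cox, common time, averaged exact ties | 1.61–1.70 |
| Cox, common time, Efron ties | 1.54–1.67 |
| Cox, common time, Breslow ties | 1.35–1.47 |
| Cox, times unrelated to case status | 1.36–1.49 |

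The estimate also moves with the split, as the algebra predicts (these splits were run on seven of the distributions). At 20 cases v 30 controls, Efron gives 1.65–1.79 and Breslow 1.45–1.62. At 30 v 20 they give 1.47–1.59 and 1.27–1.38.

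Repeat 25 v 25 runs over seven score distributions gave Efron 1.55–1.72 and Breslow 1.35–1.50, so the ends of the ranges are good to about 0.05.

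**Error rates.** With a true odds ratio of 1.0, logistic regression and Cox with discrete, averaged exact or Efron ties each reject in 0.04–0.05 of samples; Breslow rejects in 0.00–0.01. At odds ratio 2.0, Efron power is within 0.04 of logistic for every distribution.

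**The case against.** *Cox software can fit the right model.* With a constant time and strata for matched sets, or with the discrete tie likelihood, it reproduces conditional logistic regression, and the plan does promise to allow for age matching. This is true, but the result is then an odds ratio. The plan states neither device, and E.1.1 describes matching to the case population with no sets to stratify on.

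*A nested case-control study can estimate a hazard ratio.* It can when controls are sampled from those at risk at each event time. Here they are sampled on age.

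*A time-to-onset analysis may have been meant.* Aim 1 does speak of temporal relationships and incident hyperglycemia, and Aim 2's endpoint (any post-surgery glucose above 140 mg/dl) could be timed. That wording does not replace the ICU-arrival case definition, and no event time is set in either place. The cited publications were not available to check, but they cannot supply this study's event time.

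*Little depends on it.* Much of this stands. The same paragraph plans t, chi-square and rank tests that need no event time, and Aim 1.3 adds a network analysis of glucose, metabolites and biomarkers. No sample size or decision rule uses the Cox model. What is lost is the per-unit score estimate and the regression on the HOMA surrogates. The simulated figures describe one possible implementation and are not a forecast of this study's bias.

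**Conclusion.** The concern holds. The named model does not fit the outcome as defined, and this is an error in the specification, beyond missing detail. If everyone is given one dummy time, the estimate is pulled toward 1 relative to the odds ratio by an amount that depends on the tie rule and the case:control split. Under the assumed odds ratio of 2.0 and a 25 v 25 split, the usual tie rules give roughly 1.35 to 1.70. Those sizes rest wholly on assumed inputs; that the hazard ratio is undefined does not.

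The consequence is limited to the Aim 1.1 score and HOMA analyses. False-positive risk is not raised. The metabolite and pathway objective that E.1.9 names as the main one for Aim 1, and the Aim 2 trial, are untouched. It should be corrected before analysis.

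**What to change.** Rewrite the regression sentence in Aim 1.1:

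- **Case status.** Use logistic regression and report the odds ratio per score unit. State how controls are matched. If individually, use conditional logistic regression on the matched sets; if to the age distribution of the cases, use unconditional logistic regression with age, gender and smoking as covariates. The latter has four terms for an inferred 25 cases, about 6 per term (25/4), so report the unadjusted estimate beside it and read the adjusted one with caution.
- **Which sample.** For the predictive question raised under Aim 1's Potential Pitfalls, name a sample taken before ICU arrival.
- **Biomarker change after surgery.** The plan's main hypothesis is that hyperglycemia raises the biomarkers. The linear mixed models already named in Aim 1.2, by case status, would address it directly.
- **HOMA-IR or HOMA-B as outcome.** Use linear regression, on the log scale if skewed.
- **If time to event was intended.** Define origin, event and censoring before analysis, and state how controls relate to those at risk.

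The cost is analysis-plan wording only. Patients, samples, data and software stay the same.

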and intra-op at 15 minutes (after cardiac bypass has started for on pump surgeries) or 2hrs after sternum incision (for off pump surgeries), 24hrs, 72-96hrs and 30 days after surgery. Plasma samples will be stored at -80°C until analysis. The methods use UPLC with ultra-high resolution mass spectrometry with a dual chromatography, dual ionization approach with each sample being analyzed with three technical replicates.¹²²⁻¹²⁴ With advanced data extraction provided by xMSanalyzer and apLCMS, I will be able to also measure a spectrum of high and low abundance metabolites. We will utilize a well-established computational metabolomics workflow with rigorous standard operating procedures outlined in Fig. 7.¹²⁴ Data Selection and Annotation (Biostatistics and Bioinformatics Tools): HRM data will be processed using apLCMS with xMSanalyzer^{125,126}. Feature annotation will be performed using xMSannotator.¹²⁷ xMSannotator provides confidence scores for more than 2,000 metabolites, with more than 300 metabolites having confirmed identities and including most major pathways. The quality of data will be judged based on established rigorous criteria (e.g. coefficient of variation within replicates and QC samples, the percentage of missing values, the percentage of data exceeding detection limits of the machinery, batch-effects, and the percentage of outliers, etc.). Principal Component Analysis (PCA) will be used for batch-effect evaluation and ComBat¹²² will be used for batch- effect correction if necessary. Identifying expressed metabolites across different time points: we will use univariate and multivariate statistical methods, such as linear mixed effects models with post-hoc Tukey tests, LIMMA, and multilevel sparse Partial Least Squares Discriminant Analysis (msPLSDA).^{128,129} Multiple hypotheses testing correction will be performed using the Benjamini-Hochberg method.¹³⁰ Identifying putative biomarkers: we will use a consensus feature selection approach such that metabolic signatures identified by both univariate and multivariate approaches will be used for downstream analyses. K-fold and leave-one-out cross-validation using Support Vector Machine (SVM) will be performed to evaluate predictive accuracy of putative biomarkers. Two-way hierarchical clustering analysis will be performed to identify clusters of correlated metabolic features and to evaluate the ability of the discriminatory features to separate samples based on stress-hyperglycemia. Pathway enrichment analysis: Pathway analysis will be performed with pathway enrichment software for untargeted metabolomics data (Mummichog and MetabNet)^{131,132}. Where appropriate, additional chemical verification will be performed for significant metabolites of interest according to retention time and characteristic ion dissociation (MS/MS) patterns relative to authentic standards. Metabolome-wide association study (MWAS) of specific metabolites will be conducted (MetabNet) to facilitate detection of their related metabolic pathways and network structures in association with glucose levels (continuous) and stress-hyperglycemia as a discrete dichotomous variable.

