Analysis: The primary endpoint of Aim 2 is the frequency of stress-hyperglycemia ($BG > 140$ mg/dl) requiring insulin therapy during the postoperative period (Aim 2.1). We will use two-sided Chi-square test or Fisher's exact test for the primary outcome. In Aim 2.2 we will compare the difference in mean BG upon ICU arrival and the frequency of rescue therapy with SC insulin after transition to regular floor. We will also explore differences in complications between groups. Secondary outcomes of interest can be a binary outcome (e.g. whether CII is needed in ICU), or a count outcome (e.g. number of perioperative complications), or a continuous outcome (e.g. mean ICU BG concentration). We will adopt the same strategy proposed for the primary outcome to analyze any binary secondary outcomes. For secondary outcomes measured as counts, we plan to use nonparametric tests such as Krustal-Wallis tests. Univariate Poisson regression (or Negative Binomial regression) will be performed to estimate the marginal treatment effect. In addition, we will also conduct multivariate Poisson regression (or Negative Binomial regression) to assess the outcome differences between the two study groups with potential confounders considered. For secondary endpoints that produce continuous outcomes, we will use two-sample t-tests or nonparametric Wilcoxon tests to compare study groups.

Transformations will be applied if normality violation is detected.

Aim 2.3. To compare changes in metabolites and biomarkers in response to dulaglutide or placebo (measured in Aims 1.1 and 1.2), as well as beta-cell function and insulin resistance estimates.

Methods: Biomarkers and assessment of candidate metabolites will follow the same procedures as specified in Aim 1. Surrogates of beta cell function and insulin resistance will be derived from glucose, insulin, and c-peptide measurements acquired during the perioperative period.

[figure not shown]

Figure 8. Treatment groups in Aim 2. Patients will be assigned to receive dulaglutide or placebo 1-3 days before surgery.

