Analytic Techniques: Glucose levels will be analyzed by the hexokinase method (Beckman-Coulter, Los Angeles, CA). Insulin and C-peptide levels will be measured by two-site sequential chemiluminescent immuno-metric assays as previously described. Surrogates of beta cell function (HOMA-B) and insulin resistance (HOMA-IR) will be derived from fasting glucose, c-peptide and insulin. Only glucose and c-peptide will be measured serially after surgery (given high likelihood of exposure to exogenous insulin).

Analysis: We will integrate analyses from Aims 1 and Aims 2 to evaluate the role of dulaglutide on metabolites, metabolic pathways and biomarkers. We will use univariate and multivariate statistical methods, such as linear mixed effects models with post-hoc Tukey tests, LIMMA, and multilevel sparse Partial Least Squares Discriminant Analysis (msPLSDA), as described in Aim 1.

Expected outcomes in Aim 2: In Aim 2.1 we expect to observe a decrease in the number of patients with stress-hyperglycemia with low risk of hypoglycemia with dulaglutide therapy. We expect to find a least an 18 mg/dl (1 mmol/l) mean difference in BG between groups during ICU stay. In Aim 2.2 we don't expect to find differences in hospital outcomes. In Aim 2.3 We expect to observe differential changes in up or down regulation of metabolic pathways in response to dulaglutide compared to placebo.

Potential Pitfalls, and Possible Solutions, Alternative Consideration: Recruitment and retention of patients are important challenges in RCTs; however, Emory University and affiliated hospitals serve as cardiovascular referral center to a large population in the city of Atlanta, with over 1,000 major cardiac surgeries performed yearly. In our previous trial we recruited 340 patients over 3 years, therefore we expect to have enough time during the award period to complete enrollment (please see research timeline). It is possible that dulaglutide does not have an effect on the prevention of hyperglycemia. This information will help us understand the contribution of the incretin pathway to glucose metabolism during surgical stress.

E. Risks to Human Subjects

E.1.1 Human Subjects Involvement, Characteristics, and Design

- Description and justification for proposed involvement of human subjects:**

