- **Group Assignment / Case Definition:** Clinically stable adults scheduled to undergo coronary artery bypass graft surgery (CABG) will be studied. For logistic purposes recruitment will favor assignment to the clinical trial in the beginning of the award period (Aim 2, N=60). We expect a total of 30 subjects will be randomized to each group (dulaglutide or placebo). Thirty patients assigned to placebo in the clinical trial will contribute to the cohort of patients to be included in the nested case-control study. Cases and controls will be categorized prospectively on arrival to the surgical intensive care unit (SICU) (Cases are defined as BG >140mg/dL on ICU arrival). To further avoid selection bias, 25 age-matched controls will be selected for comparison. Once the number of cases is completed, additional potential controls will be selected (+/- 3 years) based on the characteristics of the population of cases. If additional patients develop stress hyperglycemia no further samples will be collected. This design will allow for efficient recruitment from our cohort of CABG patients to allow substantial savings in cost and time.
- **Research Sites:** All human subjects' research will be performed on the campus of Emory University, Atlanta, GA, and at Emory Affiliated Hospitals. Sites include Clinical Research Units (CTSA) where samples will be stored. Data collected are kept confidential and protected as per HIPAA regulations. Data collected at each facility will be shared only with the study team.

E.1.2. Study Endpoints and Sources of Materials:

- In the case control study (Aim 1) we will compare metabolic and hormonal profiles between subjects that develop stress hyperglycemia compared to controls. In an open-label format (Aim 2) we will assess whether exposure to dulaglutide is associated with a reduction in the frequency of stress hyperglycemia compared to placebo (primary endpoint). Prospectively, we will assess the association of candidate metabolites and metabolic pathways with the onset of stress hyperglycemia. Potential mechanisms underlying these associations will be explored by examining whether the associations of exposure to dulaglutide and prevention/improvement of glycemic control can be explained by changes in metabolic pathways (and key metabolites within these pathways) measured in plasma that occur between 3 days prior to surgery (baseline) and during the perioperative period. Addressing these research questions

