- Data collection and data entry. Study members will enter baseline and daily data for this study into data collection paper forms and into an electronic database provided by the Emory Research Information Technology Department. Baseline data will include demographics/history form (subject gender, date of birth, ethnicity, dates of hospitalization and operation, history of diabetes, and comorbid conditions, body weight, BMI, smoking status, type of surgery, APACHE score. Daily information will be collected on treatment (insulin IV or SC and dosage, antibiotics, use of corticosteroids), nutrition support, BG and laboratory values, hospital complications and adverse events, and length of ICU and hospital stay.

E.1.3. Potential Risks

- **Potential Risks/Discomforts:**
 - a. Venipuncture: There is some minor discomfort and risk of mild bruising during venipuncture. Standard sterile techniques will be used during phlebotomy; thus, infection is unlikely. Disposable pre-sterilized needles and syringes will be used for all blood drawing in this study; needles and syringes will not be reused. Discomforts associated with venipuncture are rapidly reversible. Approximately 40 mL of blood will be obtained for all the blood measurements proposed.

- b. Hypoglycemia: In our previous ICU studies, we observed that <10% of cardiac surgery subjects during CII and 20-30% during SC insulin experienced hypoglycemia. No episodes of severe hypoglycemia were observed during CII in our study. The use of insulin in combination with GLP1-RA may increase the risk of hypoglycemia. The number of mild (≤ 70 mg/dL) and severe hypoglycemia (≤ 40 mg/dL) and clinical consequences (neurological and cardiovascular) will be compared between groups. Treatment of hypoglycemia: hypoglycemia, defined as a BG <70 mg/dL will be treated by a standard hypoglycemia protocol available at each hospital.
- c. Hyperglycemia: it is very likely that a high proportion of patients randomized to placebo develop hyperglycemia. All subjects with hyperglycemia (in both groups) will be treated by standard protocols in the ICU units at each hospital. We expect that ~50-60% of subjects randomized to placebo will experience one or more episodes of hyperglycemia. The frequency of severe hyperglycemia will be analyzed statistically.

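### The intraoperative sample is timed differently in on-pump and off-pump patients and no Aim 1 or Aim 2.3 analysis names pump status, which can confound the case-control contrast and costs the randomized contrast precision.

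*Combined protocol and SAP*

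**What the plan says.** - **Sampling (D1, Aim 1.2 Methods).** There are five samples: baseline, intraoperative, 24 hours, 72 to 96 hours and 30 days. The intraoperative one is drawn "at 15 minutes (after cardiac bypass has started for on pump surgeries) or 2hrs after sternum incision (for off pump surgeries". The text after Figure 7 repeats the rule: "and intra-op at 15 minutes (after cardiac bypass has started for on pump surgeries".
- **Case status and matching (E.1.1, Group Assignment / Case Definition).** A case has glucose above 140 mg/dl on ICU arrival. For comparison, "25 age-matched controls will be selected for comparison", within 3 years. No other matching factor is given.
- **Aim 1.1 Analysis.** The biomarker regression is run unadjusted and "in models adjusted by gender, and smoking status".
- **Aim 1.2 analysis.** The methods offered include "linear mixed effects models with post-hoc Tukey tests, LIMMA" and multilevel sparse PLS-DA. No covariates are listed.
- **Aim 2.3.** "Biomarkers and assessment of candidate metabolites will follow the same procedures as specified in Aim 1". The same statistical methods are to be used, "as described in Aim 1", again without covariates.
- **Analysis paragraph before Aim 2.3.** Unnamed confounders are allowed for, but only in Poisson or negative binomial models of count outcomes.
- **Baseline data (E.1.2, Data collection and data entry).** The form includes "body weight, BMI, smoking status, type of surgery, APACHE score". No analysis refers to the surgery-type item.

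Pump status appears in no matching rule, stratification, covariate list or model.

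**The concern.** The plan separates on-pump from off-pump patients when it times the draw, then does not mention the distinction again. A sample taken 15 minutes into bypass and one taken 2 hours after incision without bypass differ in bypass exposure and in reference event. Any analyte that responds to either will differ between the two groups of patients for reasons unrelated to stress hyperglycemia or dulaglutide.

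This matters most for Aim 1. Case status is fixed on ICU arrival, so the intraoperative sample is the only one taken between the start of surgery and case classification. Aim 1 sets out to test temporal relationships and expects its serial samples to support causal interpretation, so this sample carries a good part of that argument.

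Two features of the plan do not remove the problem. A subject effect in a mixed model absorbs differences that are constant over time, but a shift confined to one time point is a pump-by-time effect and stays in the group contrast. Benjamini-Hochberg control deals with chance findings, not confounding, and the fallback to raw p < 0.05 for pathway enrichment would carry confounded features forward.

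**Working it through.** **Inputs from the protocol.** Aim 1: N = 50 with 25 matched controls, taken as 25 v 25; effect size above 1, alpha 0.05, power 0.80 (E.1.9; two-sided assumed). Aim 2: 30 v 30 (E.1.1).

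**Inputs assumed, because the protocol does not give them.** Pump effect D of 0.5 to 2 residual SD at the intraoperative sample; on-pump shares as shown. The five-sample schedule is taken to apply to biomarkers as well as metabolites.

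**1. The plan's own figure.** At effect size 1 the normal approximation requires 16 per group, or 17 for a Wilcoxon test (relative efficiency 0.955). With 25 per group the power is Φ(1 × √(25/2) − 1.96) = Φ(1.58) = 94%, or 93% for Wilcoxon. The plan's statement that N = 50 is adequate holds for a single unadjusted test. The present point disputes no stated number.

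**2. Case-control contrast, 25 v 25.** With no true difference, the expected spurious difference is D × (on-pump share in cases − share in controls). For example, 1 SD × (0.60 − 0.40) = 0.20 SD. Simulated two-sample t-tests (20,000 replicates, residual SD 1) gave these results. Each cell shows bias in SD, then the false-positive rate at nominal 5%:

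| On-pump share, cases v controls | D = 0.5 | D = 1 | D = 2 |
|---|---|---|---|
| 50% v 50% | 0; 5.0% | 0; 4.9% | 0; 5.0% |
| 60% v 40% | 0.10; 6.5% | 0.20; 9.8% | 0.40; 17.5% |
| 70% v 40% | 0.15; 8.0% | 0.30; 15.4% | 0.60; 32.9% |
| 80% v 40% | 0.20; 10.5% | 0.40; 24.6% | 0.80; 54.1% |

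With pump status as a covariate (least squares, 4,000 replicates), the rate was 4.4% to 5.8% in every cell, which is nominal within simulation error.

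**3. Case-control contrast, equal shares.** Only noise is added. With 30% off-pump and D = 1, the SD factor is √(1 + 0.3 × 0.7) = 1.10, so an effect size of 1 becomes 1/1.10 = 0.91. Power at 25 per group is Φ(0.91 × √12.5 − 1.96) = Φ(1.25), about 90%, or 88% for Wilcoxon. Both remain above the planned 80%.

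**4. Randomized contrast, 30 v 30.** The difference in on-pump share has mean 0 and SD √(2p(1 − p)/30), which is 0.118 at p = 0.3 or 0.7 and 0.129 at p = 0.5. The exact binomial chance of an imbalance of 20 points or more is 12.0% and 15.5% respectively. In simulation the unadjusted bias was 0 and the false-positive rate about 5% throughout.

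The cost is precision. The SD factor √(1 + D²p(1 − p)) runs from 1.10 (D = 1, p = 0.3) to 1.41 (D = 2, p = 0.5). For an illustrative 0.8 SD treatment effect:

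- Pump status accounted for: Φ(0.8 × √15 − 1.96) = Φ(1.14) = 87%.
- Ignored, factor 1.10: Φ(3.098/1.10 − 1.96) = Φ(0.86) = 80%.
- Ignored, factor 1.41: Φ(3.098/1.414 − 1.96) = Φ(0.23) = 59%.

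**The case against.** The strongest reply has five parts.

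1. *The randomized comparison is not biased.* A reader might infer that pump effects distort the dulaglutide contrast as they can distort the case-control one. They do not: allocation balances pump status in expectation. Systematic bias would need pump use to depend on assignment. E.1.2 calls Aim 2 open-label, but the documents do not say how or when pump use is decided, so that reading has no support. This stands in full.

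2. *The plan does not say it will pool.* The methods are introduced as examples and no model formula is written, so one might call this missing detail. That stands in part. But the plan's own sampling rule creates the two groups, and an analyst who applied the text as written would have no pump term.

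3. *The affected sample is one of several taken under stress.* A reader might infer that it is the only one. Section C.3 says cortisol, inflammatory and oxidative stress markers rise for several days, so the 24-hour and 72-to-96-hour samples also reflect the stress response. This stands. What remains true is that it is the only intraoperative sample.

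4. *The covariate may not exist yet.* The surgery-type item on the baseline form is not shown to separate on-pump from off-pump. This stands, although staff must know pump status to time the draw.

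5. *Two anchors are unavoidable and the work is exploratory.* Off-pump patients have no bypass start, so the sampling rule itself is not at fault. The incision-to-bypass interval is not given, so the difference in elapsed surgical time cannot be computed. Both are fair, but neither argues against adjusting the analysis.

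**Conclusion.** The point holds as a conditional one. At the intraoperative time point the plan combines samples with different anchors and names no way to account for pump status. In the case-control contrast this can confound metabolite and biomarker differences if, and only if, on-pump share differs between cases and controls and the analyte responds to bypass or timing. Age matching and adjustment for gender and smoking do not address that. In the randomized Aim 2.3 contrast the consequence is lost precision and a risk of chance imbalance.

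The size cannot be established from the documents. The range of 0.1 to 0.8 SD in step 2 rests wholly on assumed shares and effects, and the bias is zero if shares are equal. If off-pump surgery is rare at these sites, the matter is minor.

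The reach is limited. The other four samples each follow one timing rule, and the Aim 2 primary endpoint rests on postoperative glucose. A reader should not conclude that the trial's main comparison is threatened. This is a cheap improvement to the metabolite and biomarker analyses.

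**What to change.** 1. Record on-pump or off-pump status as its own field, and report it by case status and by treatment arm.
2. Include it, with its interaction with time point, in the linear mixed and LIMMA models of Aims 1 and 2.3. For Aim 2.3, use the pump status planned before randomization if it is available, so that the covariate cannot be affected by assignment.
3. For methods that take no covariate (t, Mann-Whitney and χ² tests, sparse PLS-DA, SVM, clustering, network tools), stratify by pump status or pre-adjust the intraoperative values.
4. Report the intraoperative contrast in on-pump patients alone as a sensitivity analysis.

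The cost is one data field, one or two degrees of freedom in the models, and a little extra analysis for the multivariate tools. The on-pump-only analysis uses fewer patients, so it should be read for consistency with the main result rather than tested on its own. Neither the sampling schedule nor the sample size needs to change.
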